**** Due to the recent safety signal, the study was fully unblinded to ensure the safety monitoring of the participants.***

Maternal participants 15 to 49 years of age (YOA) (inclusive, at the time of the study intervention administration) will be enrolled to receive either RSV maternal (RSV MAT) vaccine (120 µg of RSVPreF3) or the placebo control, between the 24^{0/7} to 36^{0/7} weeks of gestation (inclusive).

Approximately 378 eligible maternal participants will be enrolled* and randomized (2:1) to receive either RSV MAT vaccine or the placebo control. At least eighteen (5%) of the enrolled and randomized maternal participants will be between 15 and 17 YOA, inclusive. At the same time, infant participants (as yet unborn) will be further randomized (1:1:1) into sub-cohorts for blood sample collection for the assessment of immunogenicity at one of 3 timepoints (Day 43, Day 121 or Day 181 post-birth).

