³ Recording will be done at Visit 1, upon maternal participant randomization but the eCRF entry will be done on the demography screen.

⁴ For safety visit or RSV-associated MA-RTI visit, eDiary entries should be reviewed only if the visit occurs between Day 1 and Day 31.

⁵ RSV-associated MA-RTI unscheduled visit should be planned if the maternal participant has any symptoms or signs as defined in Section 8.4.3.1.

⁶ **In addition to the monthly contacts between Visit-2 and the Delivery visit, additional not pre-specified contacts and/or visits can be made more often (at any desired frequency), as per investigator's, maternal participant's or LAR's discretion.**

⁷ **Due to the change in the study requirements, RTI surveillance/ assessment for the maternal participants will no longer be performed**

⁸ **Placental tissue samples will be collected at delivery from all maternal participants, whenever feasible. These samples may be tested to support possible safety assessments, if necessary. Additional details are provided in the study procedures manual (SPM).**

Note:

Contact may be via telephone, SMS, email, video-telephone/telemedicine or other means, depending on local best practice. If the study site is the participant's primary healthcare facility, contact with study personnel may also be made in the context of a visit for routine or event-driven care.

The timing of an event-driven site visit (e.g., to further evaluate a potential (S)AE or RSV-MA-RTIs) cannot be defined with precision in the protocol. Event-driven visits may occur throughout the study.

In times of special circumstances, refer to Section 8 for study procedures.

CONFIDENTIAL

214725 (RSV MAT-012)
Protocol Amendment 1 Final

Table 2 Schedule of activities (SoA) – Infant participants (Amended 15 March 2022)

Visit / Contact	V1-NB	Safety contact (recommended) 5	V2-NB	C1-NB	V3-NB	V4-NB	C2-NB	V5-NB	RTI Surveillance		Notes
									Contacts (Section 8.4.2.2.1)	Visit	
Age of infant		8 days	6 weeks	3 months	4 months	6 months	9 months	12 months			
Visit Day	Birth	D8 Post-birth	D43 Post-birth	D91 Post-birth	D121 Post-birth	D181 Post-birth	D271 Post-birth	D366 Post-birth	Birth to Day 366 Post-birth	Event-Driven	
Check inclusion / exclusion criteria	•										Sections 5.1.2 and 5.2.2
Re-consent / Consent for infant participation if required by local regulations	•										
Record infant participant study number	•										
Record sub-cohort for immunogenicity assessment	•										Section 6.3.2

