10.2. Appendix 2: Clinical laboratory tests

10.2.1. Protocol-required safety laboratory assessments (Amended 15 March 2022)

Laboratory assessments detailed in [Table 24](#) should either be available as part of the routine care within 15 days prior to study intervention administration or be performed within the same interval at the local laboratory as part of screening.

Table 24 Protocol-Required Safety Laboratory Assessments

Laboratory assessments	Parameters
Hematology	Leukocytes (White Blood Cells)
	Lymphocytes
	Eosinophils
	Basophils
	Hemoglobin
	Hematocrit
	Platelets
	Neutrophils
Clinical chemistry	Alanine Aminotransferase (ALT)
	Aspartate Aminotransferase (AST)
	Creatinine
	Blood Urea Nitrogen (BUN)/urea]*
Urinalysis by dipstick	Glucose
	Protein

Notes:

* Sites not able to directly test for BUN, will test for urea and then convert urea values into BUN using the applicable established conversion factor(s).

Laboratory assessments (e.g., placenta pathology) may be performed on the placental tissue samples collected from maternal participants at delivery visit to support possible safety assessments, if necessary. Additional details are provided in the study SPM.

Additional assessments on the placental sample can be performed depending on local standard of practice, site capability and the investigators' medical judgment.

10.2.2. Descriptions of the assays to be performed in the study (Amended 15 March 2022)

Assay descriptions could be subject to change, due to assay re-development and/or qualification.

RSV-A and RSV-B neutralization assays

The serum neutralization assay is a functional assay that measures the ability of serum antibodies to neutralize RSV entry and replication in a host cell line.

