All levels	
Clinical Definition A: Maternal fever ≥ 38 degrees Celsius on one occasion plus one or more of:
 
 • Baseline fetal tachycardia (FHR > 160 bpm for 10 min or longer, excluding accelerations, decelerations and periods of marked variability or, where continuous monitoring is not available, an FHR exceeding 160 bpm during and after at least 3 consecutive contractions) • Maternal WBC $\geq 15,000$ per mm³ in the absence of corticosteroids. • Definite purulent fluid from the cervical os. 
Clinical Definition B Maternal fever ≥ 38 degrees Celsius on one occasion plus 2 of:
 
 • Maternal tachycardia (HR > 100 bpm) • Baseline fetal tachycardia (FHR > 160 bpm for 10 min or longer, excluding accelerations, decelerations and periods of marked variability or, where continuous monitoring is not available, an FHR exceeding 160 bpm during and after at least 3 consecutive contractions) • Purulent fluid from the cervical os. • Uterine tenderness • Maternal WBC $\geq 15,000$ per mm³ in the absence of corticosteroids 
Histologic diagnosis:
 
 • Positive finding of invasion of maternal polymorphonuclear leukocytes into the placental plate, the chorion and/or amnion which meets criteria based on a widely accepted histopathologic staging and grading system [such as Blanc¹ Redline², or Salafia³ criteria]. 
Culture criteria:
 
 • Positive culture of amniotic fluid (via amniocentesis), and/or • Positive culture of placental membranes (between chorion/amnion) 
GAIA gestational age level 1–2 criteria denote higher gestational age certainty including a combination of certain last menstrual period (LMP), first or second trimester ultrasound or first trimester exam confirmation. Level 3 diagnostic certainty for gestational age has a lower accuracy compared to levels 1–2. (see Section 10.8)

1a	
Clinical Definition A AND Confirmation via histopathology or culture AND Gestational age ≥ 22–0/7 weeks by GAIA gestational age level 1–2 criteria

1b	
Clinical Definition A AND Confirmation via histopathology or culture AND Gestational age ≥ 22–0/7 weeks by ANY GAIA gestational age criteria

Level	Description
2a	Clinical Definition A OR Chorioamnionitis via histopathology or culture AND Gestational age \geq 22–0/7 weeks by GAIA gestational age level 1–2 criteria

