	
Number and percentage of maternal participants reporting pregnancy-related AESIs * and worsening of pre-existing medical conditions and/or obstetric complications from Day 1 up to 42 days post-delivery. * These include maternal death, hypertensive disorders of pregnancy (gestational hypertension, pre-eclampsia, pre-eclampsia with severe features including eclampsia), fetal growth restriction, gestational diabetes mellitus, pathways to preterm birth (premature preterm rupture of membranes, preterm labor, provider-initiated preterm birth) and chorioamnionitis.
	
The number and percentage of maternal participants reporting each pregnancy-related AESI and worsening of pre-existing medical conditions and/or obstetric complications from Day 1 up to 42 days post-delivery will be tabulated with its exact 95% CI by group.
 
By participant listings of pregnancy-related AESIs and worsening of pre-existing medical conditions and/or obstetric complications will be prepared.

CONFIDENTIAL

	Primary Safety Endpoints	Statistical Analysis Methods
Infant participants	
Number and percentage of infant participants reporting neonatal / infant AESIs * from birth up to 42 days post-birth.
 
* These include small for gestational age, low birth weight including very low and extremely low birth weight (<2500 g, <1500g, <1000g), congenital anomalies (major external structural defects, internal structural defects, functional defects), neonatal death (in an extremely preterm birth [22<GA<28 weeks], in a preterm live birth [28<GA<37 weeks], or in a term live birth) and preterm birth.
	
The number and percentage of infant participants reporting each neonatal / infant AESI from birth up to 42 days post-birth will be tabulated with its exact 95% CI by group.
 
By participant listings of neonatal / infant AESIs will be prepared.

	
Number and percentage of infant participants reporting SAE, (S)AEs leading to study withdrawal, and MAEs from birth up to 42 days post-birth.
	
The number and percentage of infant participants reporting:
 
 • at least one SAE • at least one (S)AE leading to study withdrawal • at least one MAE 
from Day 1 up to 42 days post-birth with exact 95% CIs will be tabulated by group and by MedDRA preferred term.
 
By participant listings of SAEs, (S)AEs leading to study withdrawal and MAEs will be prepared.

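### Placental testing is optional and partly at unblinded investigators' discretion, yet histology or culture alone can make a chorioamnionitis AESI: show cases by basis of diagnosis and placentas tested per arm

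*Protocol*

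**What the plan says.** **Collection and testing are separate steps.** Protocol 1.3, Table 1, footnote 8 asks for near-universal collection: "Placental tissue samples will be collected at delivery from all maternal participants, whenever feasible". Testing is conditional: "These samples may be tested to support possible safety assessments, if necessary". Protocol 10.2.1 repeats that laboratory assessments such as pathology "may be performed on the placental tissue samples collected from maternal participants at delivery visit to support possible safety assessments, if necessary", and then adds: "Additional assessments on the placental sample can be performed depending on local standard of practice, site capability", and on the investigator's own judgment. Further detail is left to the study procedures manual (SPM), which is not among the documents.

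**Blinding.** Protocol 1.2 states that "the study was fully unblinded to ensure the safety monitoring of the participants". The amendment summary gives a second reason, which was to let investigators identify vaccine recipients and inform them of the risk. Protocol 6.3.5 keeps the testing laboratory blinded.

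**Case definition.** Protocol 10.9, Table 34, level 2a reads "Clinical Definition A OR Chorioamnionitis via histopathology or culture", with a gestational-age condition of at least 22 weeks. Level 2c has the same alternative under any gestational-age criteria. Dosing starts at 24 weeks, so every dosed woman meets the 22-week threshold.

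**Reporting and analysis.** Protocol 10.3.5 requires AESI reporting once there is enough evidence for the diagnosis. Chorioamnionitis is on the primary list (Protocol Table 4). SAP 4.2.1.1 tabulates by group, with exact 95% confidence intervals: "The number and percentage of maternal participants reporting each pregnancy-related AESI". Neither document plans a split by basis of diagnosis or a count of placentas tested.

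**The concern.** A woman with no fever or other sign becomes a case only if her placenta is examined. If the decision to examine depends on knowing the arm, the two arms are measured with different intensity, and the percentages in the AESI table mix disease with ascertainment. The blinded laboratory protects the reading of a sample, not the choice of which samples are sent.

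This matters because Amendment 1 added placental sampling to help understand the safety signal seen in the RSV MAT-009 study. Chorioamnionitis is an obvious result to look at beside preterm birth. A difference caused by testing, or a real difference masked by testing, would weaken the evidence the samples were meant to supply.

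**Working it through.** **The plan's own figure.** Neither document gives a figure for chorioamnionitis. The only safety precision statement (Protocol 9.2.1, SAP 5.1) is the chance of seeing at least one event among 252 vaccinees, 1 − (1 − p)^252. For p = 0.5%, 1% and 1.5% this gives 71.7%, 92.1% and 97.8%, matching the stated 72%, 92% and 98%. It says nothing about ascertainment.

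**Inputs from the documents.**
- Planned arms of 252 and 126 (Protocol Table 5). Enrollment stopped early and the number enrolled is not given.
- Dosing stopped on 25 February 2022 (Protocol 2.3) and Amendment 1 is dated 15 March 2022. Only deliveries after implementation fall under study placental collection.

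**Inputs that must be assumed.**
- f: fraction of deliveries after implementation, taken as equal in both arms.
- h: proportion of tested placentas positive on histology or culture without clinical signs, taken as equal in both arms (no vaccine effect).
- t1, t0: fractions of those later placentas tested in the vaccine and placebo arms.

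**Formula.** Study testing adds f × h × t to an arm's rate. With no vaccine effect, the difference between arms is f × h × (t1 − t0).

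| f | h | t1 vs t0 | Added rate, vaccine vs placebo | Difference (points) |
|---|---|---|---|---|
| 1 | 10% | 60% vs 20% | 6.0% vs 2.0% | +4.0 |
| 0.3 | 10% | 60% vs 20% | 1.8% vs 0.6% | +1.2 |
| 1 | 5% | 50% vs 30% | 2.5% vs 1.5% | +1.0 |
| 0.3 | 5% | 50% vs 30% | 0.75% vs 0.45% | +0.3 |
| 1 | 20% | 60% vs 20% | 12.0% vs 4.0% | +8.0 |
| 0.3 | 20% | 60% vs 20% | 3.6% vs 1.2% | +2.4 |
| 1 | 10% | 20% vs 60% | 2.0% vs 6.0% | −4.0 |
| any | any | equal | equal | 0 |

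At the planned sizes the first row is 252 × 0.06 = 15.1 cases against 126 × 0.02 = 2.5. The second is 252 × 0.018 = 4.5 against 126 × 0.006 = 0.8. A smaller enrolled number changes these counts but not the percentage-point difference; f changes both.

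The −4.0 row shows how a difference can be hidden: it would cancel a true vaccine-arm excess of 4 points.

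**Cross-check with a clinical background rate.** Assume c = 2% of women in each arm are diagnosed clinically and f = 1. The arm rate is then c + (1 − c) × h × t. With h = 10% and testing of 80% against 40%, the rates are 9.8% and 5.9%, a difference of 0.98 × 0.10 × 0.40 = 3.9 points. With 50% tested in both arms and h = 20%, both rates are 11.8%.

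**Can the recorded data separate the cases?** The GAIA certainty level is recorded (Protocol Table 4, footnote 1), but levels 2a and 2c each pool clinical cases with histology- or culture-only cases. The level alone does not isolate the second kind.

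**The case against.** Several counter-arguments have weight.

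- **Most of the discretion is not arm-related.** Local practice and site capability vary by center, and center is a minimization factor (Protocol 6.3.3), so they should be roughly balanced. This stands. The route that can depend on arm is the investigator's judgment, together with the undefined necessity condition for study testing.
- **The SPM may already fix the selection rule.** The necessity wording also fits a sponsor decision on stored samples. This cannot be checked, so the fix allows for simple confirmation.
- **The effect is diluted.** Women who delivered before implementation gave no study placental sample. This stands and is why f is in the formula.
- **Some protection exists.** Narratives must support the GAIA level (Protocol 10.9), by-participant AESI listings are planned, and histology must meet an accepted staging and grading system. These help a reader examine single cases. They do not show how many placentas were tested in each arm.
- **The analysis is descriptive and vaccination has stopped.** True, but the arms will still be compared.

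Stronger readings are tempting and the documents do not support them. A reader might infer a false excess in the vaccine arm, but nothing says which arm would be tested more. A reader might take 1 to 8 points as the expected size, but that range puts every delivery under the new provision. Heavier testing of preterm placentas raises the vaccine-arm rate only if preterm birth itself differs by arm, so that route is not an effect of testing alone. The change in collection at Amendment 1 falls on both randomized arms and creates no difference by itself. Finally, a reader might want histology-only cases removed from the primary row. They meet the GAIA definitions the protocol requires, and removing them after unblinding could hide a real subclinical signal.

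**Conclusion.** The concern holds as a possibility of differential ascertainment, in either direction, and justifies a cheap improvement. Each link is in the current text: optional testing, partly discretionary; investigators who can know the arm; a case definition that a test result alone can meet; and a primary AESI tabulated without regard to testing.

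The size cannot be derived from the documents. Under the assumptions shown it is 4 points at f = 1 and 1.2 points at f = 0.3 for h = 10% and a 40-point testing gap. It is zero when testing is equal, and the sign reverses if placebo placentas are tested more. The mechanism is certain; whether testing will in fact differ by arm is unknown, and the SPM could limit it.

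**What to change.** **SAP 4.2.1.1.** Keep the GAIA-defined primary chorioamnionitis row unchanged. Add one supplementary table by arm with:
- (a) cases meeting clinical criteria at any GAIA level, naming 3a and 3b explicitly. Level 3a accepts reported feverishness and 3b has no fever, so a rule requiring Definition A or B in full would miss them;
- (b) histology- or culture-only cases, with the number of placentas tested in that arm as denominator, split by delivery before or after implementation of Amendment 1.

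Row (b) is still conditional on who was tested. It reveals unequal testing rather than correcting for it.

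**Protocol 10.2.1 or the SPM.** State that study testing of placental samples is selected by one rule applied identically to both arms, with the arm not shown on the request, or confirm that the SPM already does this.

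**Cost.** A data field recording whether the placenta was tested, one extra table and a sentence of procedure. The basis of diagnosis should be recoverable from the AESI narratives. No extra sampling is needed and no case leaves the primary count.

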10.3.1. Definition of an adverse event (AE)

An AE is any untoward medical occurrence (an unfavorable/unintended sign - including an abnormal laboratory finding), symptom, or disease (new or exacerbated) in a clinical study participant that is temporally associated with the study intervention. The AE may or may not be considered related to the study intervention.

10.3.1.1. Events meeting the AE definition

- Significant or unexpected worsening or exacerbation of the condition/indication under study.
- Exacerbation of a chronic or intermittent pre-existing condition including either an increase in frequency and/or intensity of the condition.
- New conditions detected or diagnosed after administration of the study intervention even though they may have been present before study start.
- Signs, symptoms, or the clinical sequelae of a suspected drug, disease or other interaction.
- Signs, symptoms, or the clinical sequelae of a suspected overdose of either the study intervention or a concurrent medication.
- Signs or symptoms temporally associated with administration of the study intervention.
- Signs, symptoms that require medical attention (e.g. hospital stays, physician visits and emergency room visits)
- Pre- or post- intervention events that occur as a result of protocol-mandated procedures (i.e. invasive procedures, modification of participant's previous therapeutic regimen).
- Clinically significant abnormal laboratory findings or other abnormal assessments that are present at baseline and significantly worsen following the start of the study will also be reported as AEs or SAEs.
- AEs to be recorded as solicited AEs are described in the Section [10.3.3](#). All other AEs will be recorded as UNSOLICITED AEs.

10.3.1.2. Events NOT meeting the AE definition

- Situations where an untoward medical occurrence did not occur (e.g. social and/or convenience admission to a hospital, admission for routine examination).
- Anticipated day-to-day fluctuations of pre-existing disease(s) or condition(s) present or detected at the start of the study that do not worsen.
- Pre-existing conditions or signs and/or symptoms present in a participant before the study intervention. These events will be recorded in the medical history section of the eCRF.
- Hospitalization for elective treatment of a pre-existing condition (known or diagnosed before signing the informed consent/assent) that did not worsen from baseline.
- Any clinically significant abnormal laboratory findings or other abnormal safety assessments associated with the underlying disease, unless judged by the investigator to be more severe than expected for the participant's condition.

- Disease-related events (DRE), typically associated with the disease under study. These events will be recorded in the participant’s eCRF and will be monitored by the IDMC on a routine basis.

However, if 1 or both of the following conditions apply, then the event should be reported promptly to GSK as an SAE (see Section 10.3.8):
 - The event is, in the investigator’s opinion, of greater intensity, frequency, or duration than expected for the individual participant, or
 - The investigator considers that there is a reasonable possibility that the event was related to the administration of the study intervention

10.3.2. Definition of an SAE

An SAE is any untoward medical occurrence that:	
a.	Results in death
b.	Is life-threatening Note: The term ‘life-threatening’ in the definition of ‘serious’ refers to an event in which the participant was at risk of death at the time of the event. It does not refer to an event, which hypothetically might have caused death, had it been more severe.
c.	Requires hospitalization or prolongation of existing hospitalization Note: In general, hospitalization signifies that the participant has been admitted at the hospital or emergency ward for observation and/or treatment that would not have been appropriate in the physician’s office or in an out-patient setting. Complications that occur during hospitalization are also considered AEs. The event will also be considered serious if a complication prolongs hospitalization or fulfills any other serious criteria. When in doubt as to whether ‘hospitalization’ occurred or was necessary, the AE should be considered serious.
d.	Results in disability/incapacity Note: The term disability means a substantial disruption of a person’s ability to conduct normal life functions. This definition is not intended to include experiences of relatively minor medical significance such as uncomplicated headache, nausea, vomiting, diarrhea, influenza like illness, and accidental trauma (e.g. sprained ankle) which may interfere or prevent everyday life functions but do not constitute a substantial disruption.
e.	Is a congenital anomaly/birth defect in the offspring of a study participant Refer to Section 8.3.4 for additional information.
f.	Abnormal pregnancy outcomes (e.g. spontaneous abortion, fetal death, stillbirth, congenital anomalies, ectopic pregnancy).

g. Other situations

Medical or scientific judgment must be exercised in deciding whether reporting is appropriate in other situations. Important medical events that may not be immediately life-threatening or result in death or hospitalization but may jeopardize the participant or require medical or surgical intervention to prevent one of the other outcomes listed in the above definition should be considered serious. Examples of such events are invasive or malignant cancers; intensive treatment in an emergency room or at home for allergic bronchospasm; blood dyscrasias; and convulsions that do not result in hospitalization.

